# 3.2.1 Treatment Groups

3.2.1.1 Efficacy Treatment Groups

Fixed Dose Treatment Cycle 1

For Treatment Cycle 1 data will be summarized by the randomised Dysport Dose in the study limb. Data will be tabulated by randomised study limb treatment group, as labelled and ordered below:

- Dysport 2 U/kg
- Dysport 8 U/kg
- Dysport 16 U/kg
- Dysport Combined 8 and 16 U/kg.

## Repeat Treatment

For the evaluation of repeated Dysport treatment by Treatment Cycle (Treatment Cycles 2, 3, and 4) data will be tabulated by **the planned dose to be administered to study limb in the designated Treatment Cycle.** Data will be tabulated by study limb treatment group, as labelled and ordered below:

- Dysport 4 U/kg
- Dysport 8 U/kg
- Dysport 16 U/kg
- Dysport Combined 8 and 16 U/kg.

The 4 U/kg group will include all subjects who received 4 U/kg or less.

# 3.2.1.2 Safety Treatment Groups

# Fixed Dose Treatment Cycle 1

Safety data for Treatment Cycle 1 will be summarized by the actual Dysport dose received in the study limb, as labelled and ordered below:

- Dysport 2 U/kg
- Dysport 8 U/kg
- Dysport 16 U/kg
- Dysport Combined 8 and 16 U/kg
- Total Dysport.

Subjects who received an actual dose  $\leq 6$  U/kg at Treatment Cycle 1 will be assigned to treatment group 'Dysport 2 U/kg', subjects who received an actual dose from >6 U/kg to  $\leq 12$  U/kg will be assigned to treatment group 'Dysport 8 U/kg', and subjects with an actual dose >12 U/kg will be assigned to 'Dysport 16 U/kg'. In addition, selected safety tables will be repeated for those subjects who have received an actual Dysport dose in the study limb of **exactly** 2, 8, or 16 U/kg, i.e. excluding those who did not receive precisely the dose stated and were allocated to the nearest dose group, as described above).

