2.3 Clinical Study Rationale

Previous studies have investigated the use of BTX for the treatment of upper limb spasticity in children with hemiplegia due to CP [25, 26, 27, 28, 29, 30]. The effect of a single injection of BTX, with or without additional treatments such as occupational therapy, on spasticity,

increased muscle tone, and on the level of functional ability has been compared to control groups. In the majority of these studies temporary improvements in spasticity and muscle tone were observed in the targeted muscles, providing clear evidence for the beneficial effect of BTX. However, the assessment of functional improvement following a single treatment has shown variable results in these studies. Functional improvement in upper limb is expected to manifest after a sufficiently long period of reduced muscle tone of the upper limb following multiple treatments, during which children would have the opportunity to have adequate occupational therapy, and to learn new motor skills, necessary for the achievement of their individual goals [31].

The use of BTX for the treatment of upper limb spasticity in children is well recognised [23, 32, 33]. The choice of control group in studies is usually occupational therapy, physiotherapy and/or no treatment (no placebo injection). However, for the purpose of a phase III study, these methods of control are not adequate enough to provide sufficient scientific robustness. Only one published placebo controlled study [26] has been identified in this indication. The use of placebo as a control group is considered ethically unacceptable since injection into the upper limb muscles to this paediatric population often requires anaesthesia or heavy sedation. Therefore, a low dose control group has been chosen for this study to maintain the study blinding. The dose chosen (2 U/kg) is in line with the lowest upper limb dose used in a previous Ipsen sponsored, retrospective study [34]).

Dysport is licensed in over 75 countries for various indications. It has been approved for the treatment of spasticity of the lower limbs in children (aged 2 to 17 years) with CP at doses up to 15 U/kg (with a maximum total dose of 1000 U). In some countries Dysport has also been approved for the treatment of adult upper limb spasticity at doses up to 1000 U.

CCI

[REDACTED]

PPD

[REDACTED]

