#### 1.2.1 Study Treatment

Subjects will receive a fixed dose of Dysport 2 U/kg, 8 U/kg or 16 U/kg in the study upper limb in Treatment Cycle 1 and are planned to receive Dysport 8 U/kg or 16 U/kg in subsequent treatments according to the treatment allocation by the IRS, illustrated below, and both Investigators and subjects will remain blinded throughout the study. The allocated dose will be reconstituted to a fixed volume of 1.6 mL for injection.

| Group            | Number of | Treatment              | Treatment Cycles                 |
|------------------|-----------|------------------------|----------------------------------|
|                  | Subjects  | Cycle 1 (a) | 2, 3 and 4 (a) |
| А                | 70        | Dysport 16 U/kg        | Dysport 16 U/kg                  |
| В                | 70        | Dysport 8 U/kg         | Dysport 8 U/kg                   |
| C (b) | 70        | Dysport 2 U/kg         | Dysport 8 U/kg or                |
|                  |           |                        | Dysport 16 U/kg                  |

 Table 1
 Planned Dysport Dose per Group and Treatment Cycle

 $^{(a)}$  The total dose for the study limb must not exceed 320 U in the 8 U/kg group and 640 U in the 16 U/kg group.

(b) In this group, dynamic dose dispensing will be done by IRS at Treatment Cycle 2 to maintain a balance between subjects receiving 8 U/kg and 16 U/kg.

For Treatment Cycles 2, 3 and 4, and according to subject response, if any given total dose is not tolerated, the Investigator will request a dose reduction of 50% in the IRS. CC

For Treatment Cycles 3 and 4, if any given total dose is not adequate for the treatment of the subject's upper limb spasticity, the Investigator can request a dose increase in the IRS.

dose increase is possible for those subjects who were given Dysport 16 U/kg as the subject was already given the highest dose allowed in the study. CCI

No

CCI

. If there is no need to inject the lower limbs, and only the non-study upper limb is to be injected (on top of the study upper limb), the dose in the non-study upper limb should not exceed the dose detailed in Table 3.

 Table 3
 Dysport Dose in the Non-Study Upper Limb at Treatment Cycles 2, 3, and 4

| Body Weight (kg) | Maximum Dose                   |
|------------------|--------------------------------|
| 10 to 40         | 5 U/kg, calculated up to 40 kg |

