# 2.2 Safety Population

The safety population will consist of all randomised subjects who received at least one injection of study treatment, analysed using dose actually received.

In case a subject has not received the planned dose of 1.6 ml in the study limb the actual study limb dose will be calculated based on the actual volume received.

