#### Repeat Treatment

For the evaluation of repeated Dysport treatment data will be tabulated by the actual dose received in the study limb in the designated Treatment Cycle.

Data will be tabulated by study limb treatment group, as labelled and ordered below:

- Dysport 2/4 U/kg
- Dysport 8 U/kg
- Dysport 16 U/kg
- Dysport Combined 8 and 16 U/kg
- Total Dysport.

Subjects who received an actual dose  $\leq 6$  U/kg at Treatment Cycle 1 will be assigned to treatment group 'Dysport 2/4 U/kg', subjects who received an actual dose from >6 U/kg to  $\leq 12$  U/kg will be assigned to treatment group 'Dysport 8 U/kg', and subjects with an actual dose >12 U/kg will be assigned to 'Dysport 16 U/kg'.

In addition, selected tables will be analysed **by the actual total body dose received in the designated Treatment Cycle** (in U/kg). The total body dose will be assigned based on the sum of the dose administered into each limb injected.

For the **total body dose** treatment groups will be labelled and ordered as follows:

- Dysport  $\leq$  5 U/kg
- Dysport 10 U/kg
- Dysport 20 U/kg
- Dysport 30 U/kg
- Total Dysport.

Subjects who received an actual dose from >5 U/kg to  $\leq 15$  U/kg will be assigned to treatment group 'Dysport 10 U/kg', subjects who received an actual dose from >15 U/kg to  $\leq 25$  U/kg will be assigned to treatment group 'Dysport 20 U/kg', and subjects with an actual dose >25 U/kg will be assigned to 'Dysport 30 U/kg'.

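### The SAP says Cycle 1 safety groups go to the nearest dose, but it cuts 2 against 8 U/kg at 6 rather than 5, so a child given above 5 and up to 6 U/kg is counted as control

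*SAP*

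**What the plan says.** Cycle 1 has three fixed doses. SAP 1.2.1 states: "Subjects will receive a fixed dose of Dysport 2 U/kg, 8 U/kg or 16 U/kg in the study upper limb in Treatment Cycle 1". Protocol 2.3 gives the lowest dose its role: "a low dose control group has been chosen for this study to maintain the study blinding".

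Safety is analysed by dose received, not dose assigned. Where the full 1.6 mL was not given, SAP 2.2 says that "the actual study limb dose will be calculated based on the actual volume received".

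SAP 3.2.1.2 (Fixed Dose Treatment Cycle 1) then sets the bands. Doses up to and including 6 U/kg "will be assigned to treatment group 'Dysport 2 U/kg', subjects who received an actual dose from >6 U/kg" up to and including 12 go to the 8 U/kg group, and "subjects with an actual dose >12 U/kg will be assigned to 'Dysport 16 U/kg". The paragraph ends by planning repeat tables for children who received exactly 2, 8 or 16 U/kg, "excluding those who did not receive precisely the dose stated and were allocated to the nearest dose group, as described above".

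The Repeat Treatment part of the same section uses the same cuts of 6 and 12 with a different bottom group: "will be assigned to treatment group 'Dysport 2/4 U/kg', subjects who received an actual dose from >6 U/kg". It is introduced as grouping by the dose in the designated cycle, yet its assignment sentence refers to the dose at Cycle 1.

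**The concern.** The paragraph names a principle (nearest dose group) and gives cuts that should implement it. The cut between 8 and 16 does so; the cut between 2 and 8 does not. A child in the gap received two and a half to three times the control dose, can only have been prepared from an 8 or 16 U/kg allocation or in error, and is reported as a control child.

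The 2 U/kg column is the reference for reading Cycle 1 harm, so its contents matter more than those of any other column. The grouping feeds the Cycle 1 adverse event tables, and also the laboratory, vital-sign and ECG summaries. For those three, the text of SAP 3.2.3.3 to 3.2.3.5 lists no exact-dose repeat. The tables index is blacked out, so this cannot be checked further.

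**Working it through.** **Inputs.** Cycle 1 doses 2, 8 and 16 U/kg (SAP 1.2.1); cuts 6 and 12 U/kg (SAP 3.2.1.2); injection volume 1.6 mL (SAP 1.2.1 and 2.2); leaflet doses by weight, 10 to 40 kg (SAP 8.5); 70 children per group (SAP Table 1).

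**Step 1: the cuts that a nearest-dose rule gives.** The boundary between doses a and b is (a + b)/2.

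| Pair (U/kg) | Midpoint | SAP cut |
|---|---|---|
| 8 and 16 | (8 + 16)/2 = 12 | 12, reproduced |
| 2 and 8 | (2 + 8)/2 = 5 | 6, not reproduced |
| 4 and 8 (repeat cycles only) | (4 + 8)/2 = 6 | 6, reproduced |

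The total-body-dose cuts in the same section are also midpoints: (10 + 20)/2 = 15 and (20 + 30)/2 = 25. A log scale does not rescue 6: √(2 × 8) = 4, and √(8 × 16) = 11.3 would no longer reproduce 12.

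**Step 2: who falls in the gap.**

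- At 5.5 U/kg the distance is 3.5 to the 2 U/kg dose and 2.5 to the 8 U/kg dose.
- At 6.0 U/kg the distances are 4.0 and 2.0.
- The SAP files both as 2 U/kg.

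**Step 3: how a child gets there.** Volume = 1.6 × (dose received / dose allocated).

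- Allocated 8 U/kg: 1.6 × 5/8 = 1.0 mL and 1.6 × 6/8 = 1.2 mL, so more than 1.0 and up to 1.2 mL.
- Allocated 16 U/kg: 1.6 × 5/16 = 0.5 mL and 1.6 × 6/16 = 0.6 mL, so more than 0.5 and up to 0.6 mL.

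Leaflet rounding alone never reaches the gap. Full doses run as follows:

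- 2 U/kg: 20/12 = 1.67 to 30/13 = 2.31 U/kg.
- 8 U/kg: 100/13 = 7.69 to 100/12 = 8.33 U/kg.
- 16 U/kg: 325/21 = 15.48 to 475/29 = 16.38 U/kg.

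Moving the cut to 5 therefore reassigns no correctly prepared 2 U/kg child.

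**Step 4: size and direction.** One child in 70 is 1/70 = 1.4 points. As an illustration, assume 14 of 70 control children have an event (20.0%). Adding one misfiled child gives 15/71 = 21.1% if that child had the event and 14/71 = 19.7% if not. The control rate can move either way.

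**The case against.** The best reply is that the rule is explicit and only one word is loose. No programmer could misapply the bands. The word in question sits in a later clause about a different table set, and that clause defers to the bands. Deleting it would remove the contradiction. That is true of the wording, but it would leave part-dosed 8 or 16 U/kg children in the control column, and the SAP gives no reason for wanting them there.

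Other parts of the reply stand:

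- **The gap may be empty.** Protocol 9.1.3.3 requires the whole 1.6 mL to be injected, and nothing in the documents shows that any child received a volume in the affected range.
- **The damage is limited.** Efficacy is analysed as randomised (SAP 2.1.1), safety is descriptive (Protocol 11.4.4), the exact-dose tables for adverse events and events of special interest exclude these children, and the adverse event listings show the study limb dose.
- **Common cuts have a use.** SAP 3.2.3.1 tabulates adverse events across all four cycles and combined. Changing Cycle 1 alone would give a child at 5.5 U/kg the 8 U/kg label under one rule and the 2/4 U/kg label under the repeat rule as now worded. Both texts must be edited together.
- **Some asymmetry remains.** With a cut at 5, control still admits up to 5/2 = 2.5 times its nominal dose, against 3 times now. The change restores the stated principle; it does not make the bands proportionate.

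A reader might infer that the cut systematically inflates harm in the control column and flatters the tested doses. The documents do not support that: a misfiled child without the event lowers the control percentage. Nor is this a flaw in a randomised comparison, because grouping by dose received is not grouping as randomised.

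**Conclusion.** The inconsistency is real and lies within one paragraph: a nearest-dose rule for 2, 8 and 16 U/kg has cuts at 5 and 12, and the SAP uses 6 and 12. It affects only children above 5 and up to 6 U/kg in Cycle 1, and only summaries grouped by dose received. Few or no children may be involved, with an effect of at most about 1.4 points each in a column of 70, in either direction. This is a tidy-up worth making, not a threat to the trial's conclusions.

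The size rests on actual U/kg being computed consistently with the dosing weight. The SAP does not say which weight applies above the 40 kg cap. If true weight were used (an assumption), a full 320 U dose would fall in the gap from 320/6 = 53.3 kg to just under 320/5 = 64 kg, and the gap might not be rare. The point does not depend on this.

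It is tempting to say that 6 was carried over from the repeat cycles, where 4 U/kg exists. It fits, but the SAP does not say so.

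**What to change.** Make three linked edits before unblinding:

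1. SAP 3.2.1.2, Fixed Dose Treatment Cycle 1: up to 5 U/kg to the 2 U/kg group, above 5 up to 12 to the 8 U/kg group, above 12 to the 16 U/kg group.
2. SAP 3.2.1.2, Repeat Treatment: make the assignment sentence refer to the dose in the designated cycle instead of Cycle 1, and keep 6 as the lower cut for Cycles 2 to 4.
3. SAP 3.2.3.1: state that in the all-cycle adverse event tables Cycle 1 data are grouped by the Cycle 1 cuts.

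The cost is a few lines of SAP text, the matching change in the derivation program and its check, and a footnote. The downside is that the lower boundary of the 8 U/kg label will be 5 in Cycle 1 and 6 later, which the footnote must state. This changes an analysis grouping only; it has no bearing on the dose any child receives.

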#### Repeat Treatment

For the evaluation of repeated Dysport treatment data will be tabulated by the actual dose received in the study limb in the designated Treatment Cycle.

Data will be tabulated by study limb treatment group, as labelled and ordered below:

- Dysport 2/4 U/kg
- Dysport 8 U/kg
- Dysport 16 U/kg
- Dysport Combined 8 and 16 U/kg
- Total Dysport.

Subjects who received an actual dose  $\leq 6$  U/kg at Treatment Cycle 1 will be assigned to treatment group 'Dysport 2/4 U/kg', subjects who received an actual dose from >6 U/kg to  $\leq 12$  U/kg will be assigned to treatment group 'Dysport 8 U/kg', and subjects with an actual dose >12 U/kg will be assigned to 'Dysport 16 U/kg'.

In addition, selected tables will be analysed **by the actual total body dose received in the designated Treatment Cycle** (in U/kg). The total body dose will be assigned based on the sum of the dose administered into each limb injected.

For the **total body dose** treatment groups will be labelled and ordered as follows:

- Dysport  $\leq$  5 U/kg
- Dysport 10 U/kg
- Dysport 20 U/kg
- Dysport 30 U/kg
- Total Dysport.

Subjects who received an actual dose from >5 U/kg to  $\leq 15$  U/kg will be assigned to treatment group 'Dysport 10 U/kg', subjects who received an actual dose from >15 U/kg to  $\leq 25$  U/kg will be assigned to treatment group 'Dysport 20 U/kg', and subjects with an actual dose >25 U/kg will be assigned to 'Dysport 30 U/kg'.

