# 2.6 **Populations of Primary Interest**

For the fixed dose Treatment Cycle 1, the primary population for the efficacy analyses will be the mITT population.

Secondary populations of interest for the efficacy analyses will be the PP population and the Randomised Population.

For the evaluation of efficacy over repeated treatments, analyses per Treatment Cycle will be performed using the available data from all subjects of the mITT population in the specified treatment cycle according to the planned dose for the specified treatment cycle.

The safety analyses of the fixed dose Treatment Cycle 1 will be performed on the safety population.

For the evaluation of safety over repeated treatments, analyses per Treatment Cycle will be performed using the available data from all subjects of the safety population in the specified treatment cycle according to the actual dose received in the specified Treatment Cycle.

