#### Repeat Treatment

For the assessment of efficacy and safety over repeated Dysport treatments, the focus will be on those subjects who received 8 or 16 U/kg in the study limb. Data will be presented by Treatment Cycle and analysed according to the planned dose (efficacy) or actual dose received (safety) in the study limb in the stipulated Treatment Cycle.

As subjects can receive Dysport in the lower limb(s) and non-study upper limb from Study Treatment 2 onwards, safety over repeated Treatment Cycles will also be evaluated using the total body dose of Dysport received in the specified Treatment Cycle.

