# 3.2.3 Safety

All safety data will be included in the safety data listings and summary tables will be based on the safety population. Across all treatment cycles summary safety tables

will be presented by the dose received in the study limb in the specified Treatment Cycle. For the fixed dose Treatment Cycle 1 selected tables will also be presented by exact dose received. For analyses over repeat treatments by Treatment Cycle, selected tables will also be presented by total body dose received.

Safety tables will be presented by the treatment groups specified in Section 3.2.1.2.

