### *3.2.3.1 Adverse Events*

For AEs, the sponsor will use the latest version of Medical Dictionary for Regulatory Activities (MedDRA) in effect within the sponsor company at the time of database lock.

Adverse events will be recorded from time of informed consent until the end of study and all AEs will be considered for inclusion in the analyses.

All AEs reported during the study will be presented in a listing which will be sorted by subject identifier (subject ID), the AE start and end date, primary system organ class (SOC), preferred term (PT) and verbatim text. TEAEs will be assigned to the last Study Treatment prior to the onset of the AE. The Treatment Cycle, the Study Limb Dose, and the Total Body Dose at which each AE started will be included.

Serious AEs, AEs leading to withdrawal, death, and TEAEs will be flagged in the AE listings.

Listings of all serious adverse events (SAE), AEs leading to withdrawal and deaths reported during the study will also be presented, using the same sort order. Listings of AEs of special interest will also be provided, for remote spread of effects as well as for hypersensitivity reactions.

A TEAE is defined as any AE that occurs during the treatment phase of the study if:

(1) it was not present prior to receiving the first intake of study medication, or

(2) it was present prior to receiving the first intake of study medication but the intensity increased during the treatment phase of the study.

(3) it was present prior to receiving the first dose of study treatment, the intensity is the same but the drug relationship became related during the active phase of the study.

A TEAE that occurs under a particular treatment cycle and worsens in intensity under a different treatment cycle will be considered as treatment emergent under the two treatment cycles. In the event of another occurrence of a TEAE with a change in intensity under a different treatment cycle, the subject will also be counted in that different treatment cycle. A given AE will be assigned to the dose received prior to the onset of the AE in the designated treatment cycle.

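### SAP 3.2.1.2 assigns the low-dose column of the repeat-treatment safety tables by the Cycle 1 dose, against the SAP's own rule of using the dose of the cycle being reported

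*SAP*

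**What the plan says.** The Repeat Treatment part of SAP 3.2.1.2 defines the study-limb columns for safety tables: 2/4, 8, 16, combined 8 and 16 U/kg, and total. It opens with the rule that "data will be tabulated by the actual dose received in the study limb in the designated Treatment Cycle". It then sets the cut-offs. Subjects with an actual dose of at most 6 "U/kg at Treatment Cycle 1 will be assigned to treatment group 'Dysport 2/4 U/kg" column. Doses above 6 and up to 12 go to the 8 U/kg column, and doses above 12 to the 16 U/kg column. Only the first of these three clauses names a cycle.

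The Fixed Dose part of the same section has an almost identical sentence, where at most 6 "U/kg at Treatment Cycle 1 will be assigned to treatment group 'Dysport 2 U/kg" column. There the Cycle 1 reference is right.

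Elsewhere the SAP consistently uses the cycle being reported:

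- Section 2.6: "according to the actual dose received in the specified Treatment Cycle".
- Section 3.1, Repeat Treatment: "actual dose received (safety) in the study limb in the stipulated Treatment Cycle". The same paragraph adds that "the focus will be on those subjects who received 8 or 16 U/kg in the study limb".
- Section 3.2.3: summary tables "will be presented by the dose received in the study limb in the specified Treatment Cycle".
- Section 3.2.3.1: "A given AE will be assigned to the dose received prior to the onset of the AE in the designated treatment cycle".
- Sections 3.2.3.7, 3.2.9.2 (for Cycles 2 to 4) and 3.2.9.3 also use the dose given in the specified cycle.

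**The concern.** The opening rule and the cut-off sentence cannot both be applied in Cycles 2 to 4. The difference matters most for Group C, whose planned dose moves from 2 U/kg in Cycle 1 to 8 or 16 U/kg from Cycle 2 (SAP 1.2.1, Table 1).

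The sections that ask for these tables name the right cycle, but most of them refer back to 3.2.1.2 for the dose groups. In the text available, that is the only place where the repeat-treatment study-limb cut-offs are set. A programmer who codes the cut-off sentence would place Group C's adverse events after 8 or 16 U/kg under a low-dose label.

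Long-term safety of multiple treatments is the study's secondary objective, and these tables serve it.

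**Working it through.** **Inputs.** 70 subjects are planned per group (SAP 1.3.4). Planned doses in Cycle 1 and then Cycles 2 to 4 are: A 16 then 16, B 8 then 8, C 2 then 8 or 16 U/kg, with the Group C split kept balanced (SAP 1.2.1). A 50% reduction is possible from Cycle 2 and an increase from Cycle 3. Reconstitution leaflets exist only for 2, 4, 8 and 16 U/kg (Protocol 9.1.3.1), so the only step up from 8 is 16.

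**Are the thresholds themselves sound?** Dividing the unit doses in SAP 8.5 by body weight over 10 to 40 kg gives these ranges:

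| Leaflet | Lowest U/kg | Highest U/kg |
|---|---|---|
| 2 U/kg | 20/12 = 1.67 | 30/13 = 2.31 |
| 4 U/kg | 40/11 = 3.64 | 60/14 = 4.29 |
| 8 U/kg | 100/13 = 7.69 | 100/12 = 8.33 |
| 16 U/kg | 325/21 = 15.48 | 475/29 = 16.38 |

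Cut-offs of 6 and 12 separate these doses cleanly. Only the reference cycle is at fault.

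**Columns under three readings, for a table on a later cycle.**

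| Dose path (Cycle 1 → later) | (a) Cycle 1 dose in all clauses | (b) Cycle 1 dose in first clause only | (c) Designated-cycle dose in all clauses |
|---|---|---|---|
| C: 2 → 8 | 2/4 | 2/4 and 8 | 8 |
| C: 2 → 16 | 2/4 | 2/4 and 16 | 16 |
| B: 8 → 8 | 8 | 8 | 8 |
| B: 8 → 4 | 8 | none | 2/4 |
| B: 8 → 16 | 8 | 16 | 16 |
| A: 16 → 16 | 16 | 16 | 16 |
| A: 16 → 8 | 16 | 8 | 8 |

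Only reading (c) puts every path in exactly one column that matches the dose given.

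**Size.** Assume planned doses, full retention and an even Group C split (35/35).

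- Reading (c): 2/4 = 0; 8 = 70 + 35 = 105; 16 = 70 + 35 = 105; combined = 210.
- Reading (a): 70/70/70; combined = 70 + 70 = 140. Moved to the low-dose column: 70/210 = 33.3%.
- Reading (b): 8 and 16 stay at 105 each and combined at 210, but Group C also matches 2/4, so 70 of 210 subjects match two columns. If the clauses are coded in order and the first match is kept, the result is again 70/70/70.

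With 80% retention in every group (an assumption; 56 per group), reading (c) gives 0/84/84 with 168 combined (56 + 28 = 84). Reading (a) gives 56/56/56 with 112 combined. Moved: 56/168 = 33.3%. With 70% retention the figure is 49 of 147, the same share. At equal retention the share is one third however Group C is split.

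**The case against.** The strongest reply is that the one-third shift does not follow from the sentence as punctuated. The Cycle 1 phrase sits in the first clause only. On that reading nobody leaves the 8 or 16 U/kg columns, and the fault is a double match. This is right as far as it goes, so the one-third figure belongs to the reading that uses the Cycle 1 dose throughout. But the clause-limited reading is no better as a rule: Group C has two columns, and a subject reduced from 8 to 4 U/kg satisfies no clause.

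A second reply is that the 2/4 label suits tables spanning Cycles 1 to 4, so the phrase may be meant only for the Cycle 1 part. Then no stated cut-off covers doses of 6 U/kg or less in Cycles 2 to 4. Yet the label needs one, because a planned 4 U/kg dose arises only after Cycle 1 (SAP 1.2.1 and 3.2.1.1).

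Third, the intention is easy to infer. The opening sentence gives the rule, the table descriptions repeat it, and outputs are double programmed and reviewed (SAP 4.3). A careful programmer would probably get it right. That stands, and it keeps the point minor. It does not make the written rule correct, and two programmers working from the same sentence can make the same error.

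Fourth, SAP 3.2.9.1 does group by Cycle 1 dose on purpose. It does so only for exposure across the whole study; 3.2.9.2 returns to the specified cycle for repeat treatment.

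Finally, the table templates are a separate document and the tables index is blacked out, so it cannot be checked whether either already states the right cycle.

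**Conclusion.** The concern holds, as a minor point. The cut-off sentence is wrong as written: under either reading of the Cycle 1 phrase, Group C meets the 2/4 U/kg column in later cycles despite planned doses of 8 or 16 U/kg, and a subject reduced from 8 to 4 U/kg is misplaced or unplaced. If the Cycle 1 dose is used throughout, one third of subjects carry the wrong label (70 of 210 at full retention), assuming planned doses and equal retention across groups. Dose changes would alter the counts, and the documents do not give their frequency.

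The reach is limited to descriptive tables by study-limb dose for Cycles 2 to 4: adverse events and events of special interest (SAP 3.2.3.1), the safety subgroups (3.2.3.7) and exposure (3.2.9.2 and 3.2.9.3). Efficacy has its own groups in 3.2.1.1. Tables by total body dose and the adverse event listings are unaffected, and no test is run on repeat-treatment data.

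**What to change.** In the Repeat Treatment cut-off sentence of SAP 3.2.1.2, replace the words 'at Treatment Cycle 1' with 'in the designated Treatment Cycle', and word the sentence so that this governs all three cut-offs (at most 6, above 6 to 12, above 12 U/kg). Check the separate table templates for the same phrase. The cost is one phrase in the SAP. It needs no new data, changes no planned analysis and concerns only the assignment of table columns, not dosing.
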